7.2 Study Procedures

The study consists of one visit in clinic during their standard of care visit. Patients will be given information about the study and asked to participate. If eligible, based on inclusion and exclusion criteria, informed consent will be obtained at the time of the screening visit and the patient will be enrolled in the study.

After obtaining informed consent, the patient will be asked to rate their current pain on a visual 1-10 point scale before injection. They will then be randomized to one of three treatment groups. The study investigator will randomly draw a sealed envelope containing one of the three treatment groups. The sealed envelopes will be stored in a secure area within the clinic practice site. The subject will be randomized to one of three groups:

- Group A=Injection of 1 ml of 40 mg Kenalog combined with 4 ml of 1% lidocaine
- Group B=Injection of 1 ml of 40 mg Kenalog combined with 4 ml of 1% lidocaine after 2 ml in subcutaneous injection
- Group C=Injection of 1 ml of 40 mg Kenalog combined with 4 ml of 1% lidocaine after applying ethyl chloride spray for 3 seconds

The needle size will be standardized:

- 25 gauge needle for the subcutaneous lidocaine injection
- 21 gauge needle for the combined injection

Immediately after and ten minutes after the injection is completed, they will also be asked to rate pain on the same 1-10 visual scale.

No long-term follow-up will be conducted.

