8.2 Sample size determination

The primary endpoint is the change in visual pain scale from baseline (pre-injection) to follow up (0- and 10-minutes after injection). The study contains 3 groups:

- Group A=Injection of 1 ml of 40 mg Kenalog combined with 4 ml of 1% lidocaine
- Group B=Injection of 1 ml of 40 mg Kenalog combined with 4 ml of 1% lidocaine after 2 ml in subcutaneous injection
- Group C=Injection of 1 ml of 40 mg Kenalog combined with 4 ml of 1% lidocaine after applying ethyl chloride spray for 3 seconds

Comparisons will be made for the primary outcome between all 3 study groups: Group B vs. A; Group C vs. A; and Group C vs. B. Thus, we used a Bonferroni corrected Type I error rate for 3 tests to determine the sample size required for 80% power.

A total of N=50 patients per group (N=150 total) yields 80% power for a t-test conducted at the Bonferroni corrected Type I error rate of 1.7%, which holds the overall Type I error rate for the study at 5%, to detect a 2-point difference in pain scale changes between groups, assuming a common standard deviation of 3 points. The standard deviation was calculated after making a conservative assumption that visual pain scores would be uniformly distributed across 0-10.

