8.3 Statistical methods

A one-way analysis of variance (ANOVA) model will be used to test whether changes in pain scores differ by study group. The outcome variable for the model will be the change in pain scores, and the independent variables will be indicators of each study group. The overall F-test for study group will be used to determine whether study groups differ with respect to mean changes in visual pain scores. If the F-test is significant, then follow up tests comparing each set of groups will be conducted using the Bonferroni-adjusted Type I error rate of 1.7%.

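### The SD of 3 comes from single pain ratings but is used for the change score, so the 80% power rests on an unstated correlation that baseline adjustment would make unnecessary

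*Combined protocol and SAP*

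**What the plan says.** Section 8.2 defines the outcome as a change: "The primary endpoint is the change in visual pain scale from baseline (pre-injection) to follow up (0- and 10-minutes after injection". It states 80% power with 50 patients per arm "to detect a 2-point difference in pain scale changes between groups, assuming a common standard deviation of 3 points", using a t-test at 1.7%. The origin of the SD follows: "The standard deviation was calculated after making a conservative assumption that visual pain scores would be uniformly distributed across 0-10". On multiplicity it says: "Thus, we used a Bonferroni corrected Type I error rate for 3 tests to determine the sample size required for 80% power".

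Section 8.3, repeated in 10.7, specifies a one-way ANOVA: "The outcome variable for the model will be the change in pain scores, and the independent variables will be indicators of each study group". Baseline pain is not in the model, although section 7.2 collects it: "the patient will be asked to rate their current pain on a visual 1-10 point scale before injection". Ratings are then taken immediately after the injection and again ten minutes later.

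No section gives a correlation between baseline and follow-up or an observed SD, and section 2.2 (Previous Data) is marked not applicable. Section 16.2 mentions a calculated sample size of 138, which 8.2 does not explain.

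**The concern.** The assumption behind the SD is about pain scores, but the SD is applied to pain changes. A change contains the variability of two ratings, reduced by whatever correlation they share. A wide distribution for one rating may be conservative for that rating; it does not follow that it is conservative for the change.

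A high correlation cannot be taken for granted here. The baseline rating is of current shoulder pain, while the 0-minute rating follows a needle procedure directly and may partly reflect it. If the correlation is low, 50 per arm falls well short of 80%. The planned ANOVA is valid under randomisation, so bias and Type I error are not the issue. What is at stake is precision, and whether the stated power can be relied on.

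Section 8.2 also lists two follow-up ratings while correcting for three tests, and neither 8.3 nor 10.7 says which rating enters the model. A power figure needs one named outcome.

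**Working it through.** **Inputs.** From section 8.2: 50 per arm, a 2-point difference, SD 3, and alpha 0.05/3 per comparison. Assumed, because the documents do not say: two-sided tests, equal SDs at baseline and follow-up (varied under the objection), and one final analysis (the interim in section 10.6 is not counted). Rho and the true rating SD are not given, so ranges are shown.

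**1. The plan's figure.** Noncentrality = 2 / (3 × √(2/50)) = 3.33 with 98 df. Power is 81.3% at 0.05/3 and 81.5% at 0.017. The stated 80% is reproduced. Under this test, power falls to 80% when the SD reaches 3.045.

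**2. What 3 measures.** A uniform rating on 0-10 has SD 10/√12 = 2.89 if continuous and √10 = 3.16 if in whole numbers. The stated 3 lies between them, so it has the size of a single-rating SD. Putting 2.89 into the same t-test at 0.05/3 gives 46 per arm, or 138 in all, which is the number in 16.2. The documents do not say how 138 arose, so this only supports the reading.

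**3. SD of the change.** SD_change = SD × √(2(1 − rho)). At SD 3 and rho 0.3 this is 3 × √1.4 = 3.55. The rho needed for 80% is 1 − 3.045²/(2 × SD²): 0.44 at SD 2.89, 0.48 at SD 3 and 0.54 at SD 3.16.

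**4. Baseline as covariate.** The ANCOVA residual SD is SD × √(1 − rho²), with 97 df for a two-arm comparison. Its variance relative to the change score is (1 − rho²)/(2(1 − rho)) = (1 + rho)/2, which is 0.50, 0.65, 0.75 and 0.85 at rho 0, 0.3, 0.5 and 0.7.

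| Rating SD | Analysis | rho 0 | rho 0.3 | rho 0.5 | rho 0.7 |
|---|---|---|---|---|---|
| 2.89 | change score | 51% | 69% | 85% | 98% |
| 2.89 | ANCOVA | 85% | 88% | 94% | 99% |
| 3 | change score | 47% | 65% | 81% | 97% |
| 3 | ANCOVA | 81% | 85% | 92% | 99% |
| 3.16 | change score | 42% | 59.5% | 76.5% | 95% |
| 3.16 | ANCOVA | 76.5% | 81% | 89% | 98% |

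At SD 3 the change-score analysis needs 96, 68, 49 and 30 patients per arm for 80% at these correlations. At SD 3.16, ANCOVA reaches 80% from rho = √(1 − 3.045²/3.162²), about 0.27.

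**5. Check with the F-test gate.** A three-arm simulation was run with the F-test at 5%, then B versus A at 0.05/3, with arm C midway. At SD 3 it gave 47.7, 65.2, 81.4 and 96.9% for change scores, and 81.2% for ANCOVA at rho 0.

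**6. One rating or two.** With no true difference, ANCOVA and assumed correlations, at least one false pairwise claim occurred in 4.1-4.4% of simulated trials with one named rating. With both ratings at full alpha it occurred in 6.4-8.4%. With alpha split (F-test 2.5%, pairwise 0.05/6) it occurred in 3.3-4.2%. The split costs power: at SD 3 and rho 0, ANCOVA falls to 73.2%. The SD that gives 80% becomes 2.822, so at SD 3 rho must be at least √(1 − 2.822²/3²), about 0.34.

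**The case against.** The strongest reply is that the uniform assumption is deliberately wide. If the true rating SD is smaller, the rho needed falls quickly: 1 − 3.045²/(2 × SD²) is about 0.31 at SD 2.60 (uniform on the 1-10 scale patients use), 0.26 at SD 2.5, and zero near SD 2.15. At SD 2 the change-score analysis has 86% power even at rho 0. Unequal SDs can help too: with baseline SD 2, follow-up SD 3 and rho 0.3, the change variance is 4 + 9 − 3.6 = 9.4 and power is 79%, not 65%. The sponsor may also have had rho 0.5 in mind without writing it down.

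All of this stands as sensitivity, and it is why underpowering is not shown. It does not supply the missing justification, because the documents give neither the true SD nor a correlation. Nor does it count against the covariate. With baseline SD s0 and follow-up SD s1, the change variance equals s1²(1 − rho²) + (s0 − rho × s1)², so the ANCOVA residual variance is never larger.

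It is also true that ANCOVA leaves a condition, namely that the follow-up rating's SD is 3 or less. That condition can at least be stated openly and relates directly to the assumption the plan already makes.

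Finally, the plan does not say that both ratings will be tested at full alpha. The 6.4-8.4% is therefore a warning about how the fix is written, not a defect shown in the plan.

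**Conclusion.** The point holds and should be fixed. The 80% is correct for a change-score SD of 3, but the plan justifies 3 only as the SD of one rating. For the change-score ANOVA as written, with equal SDs, 80% requires rho of at least about 0.44, 0.48 or 0.54 at rating SDs of 2.89, 3 or 3.16. At SD 3, power runs from 47% (rho 0) to 97% (rho 0.7), so the error can go in either direction and *conservative* is not supported for the change. Baseline adjustment brings power to at least 80% at every rho if the rating's SD is 3 or less. These figures assume two-sided tests at 0.05/3, 50 evaluable patients per arm, one named follow-up rating and a single final analysis.

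**What to change.** 1. In 8.3 and 10.7, replace the ANOVA with wording such as:

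> The primary confirmatory analysis is an ANCOVA of the change in pain from baseline to the [0- or 10-]minute rating, with study group as factor and baseline pain as covariate. If the F-test for study group is significant at 5%, the three pairwise differences are tested at 1.7%.

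   Group effects and p-values are identical whether the outcome is the change or the follow-up score, so the endpoint can stay as change. These levels are for a single final analysis; any efficacy use of the interim look (10.6, 19.7) must be settled separately.

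2. Name one rating, at the sponsor's choice, to carry the F-test, the pairwise tests and the power claim. Report the other as secondary, with estimates and confidence intervals. If both must be confirmatory, split alpha and restate the power. Do not test both at full alpha.

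3. In 8.2, state that 3 is the assumed SD of one rating and that the 80% refers to the ANCOVA on the named rating, provided its SD is 3 or less. Drop *conservative* as a description of the change-score SD.

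4. Ask the sponsor how 3 was obtained and reconcile the 138 in 16.2 with 8.2. Do not write in a derivation that the documents do not give.

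The cost is wording in 8.2, 8.3 and 10.7, a check of 16.2, and one degree of freedom. No patients, visits or data are added.

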8.3 Statistical methods

A one-way analysis of variance (ANOVA) model will be used to test whether changes in pain scores differ by study group. The outcome variable for the model will be the change in pain scores, and the independent variables will be indicators of each study group. The overall F-test for study group will be used to determine whether study groups differ with respect to mean changes in visual pain scores. If the F-test is significant, then follow up tests comparing each set of groups will be conducted using the Bonferroni-adjusted Type I error rate of 1.7%.

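### Testing each pair at 1.7% behind a significant overall F-test is valid but stricter than three groups need; a closed test would add about 3 to 7 points of power for the planned 2-point difference

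*Combined protocol and SAP*

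**What the plan says.** Section 8.2 plans three pairwise comparisons, "Group B vs. A; Group C vs. A; and Group C vs. B", and states that "we used a Bonferroni corrected Type I error rate for 3 tests to determine the sample size required for 80% power". It describes a "t-test conducted at the Bonferroni corrected Type I error rate of 1.7" percent, "which holds the overall Type I error rate for the study at 5" percent, "to detect a 2-point difference in pain scale changes between groups" with a common SD of 3. Its result is that "A total of N=50 patients per group (N=150 total) yields 80% power".

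Section 8.3 puts a one-way ANOVA in front of these tests. The pairs are examined only if the overall F-test is significant, and then "follow up tests comparing each set of groups will be conducted using the Bonferroni-adjusted Type I error rate of 1.7" percent. Section 10.7, in the monitoring chapter, repeats this. Neither section gives the level of the F-test, says whether the pair tests use a pooled or a separate variance, or explains why both controls are used.

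**The concern.** By the reasoning of 8.2, the 1.7% level alone is enough to hold the overall error at 5%. Section 8.3 adds a gate that, with three groups, would be enough without the 1.7%. Using both leaves part of the permitted 5% error unspent, and the price is power.

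The comparisons of interest are the individual pairs, so power per pair is the measure that matters. Sections 2.1 and 2.3 say that if local anesthesia shows no significant effect, it could be left out to save cost. A real difference that is missed could therefore be read as support for dropping it.

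**Working it through.** **Inputs.** From 8.2: 50 per group, difference 2, SD 3, 1.7% per pair, 5% overall, three pairs. From 8.3: the F-test gate. Assumed, because the documents do not say: F-test at 5%, two-sided pair tests, normal errors. The third arm's mean is not given and was varied.

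**1. The plan's own figure.** The standard error of a difference is 3 × √(2/50) = 0.6, so the noncentrality is 2/0.6 = 3.33. With 98 degrees of freedom the two-sided 1.7% critical value is 2.43. The noncentral t gives 81.5% power (81.3% at exactly 0.05/3), and 49 per group would reach 80%. The stated 80% reproduces.

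**2. Why the gate is enough with three groups.** Consider how many of the three pairwise nulls are true.
- All three: this is the global null. No pair is tested unless the F-test rejects, so the error is at most 5%.
- Exactly two: impossible, because two equalities force the third.
- Exactly one: only that test can err, and a single 5% test errs at most 5% of the time.
- None: no Type I error is possible.

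This argument does not carry over to four or more groups.

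**3. Family-wise error by simulation** (1,000,000 trials per scenario, common SD 3, pooled error with 147 degrees of freedom).

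| True state | Plan: gate, then 1.7% | Gate, then 5% |
|---|---|---|
| All three arms equal | 4.2% | 5.0% |
| Two arms equal, third far away | 1.7% | 5.0% |

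**4. Power, same simulation.**

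| Means | Quantity | Plan | Gate, then 5% | Gain (points) |
|---|---|---|---|---|
| 0, 2, 0 | each 2-point pair | 81.9% | 89.2% | 7.3 |
| 0, 2, 0 | any significant pair | 92.3% | 93.7% | 1.4 |
| 0, 2, 1 | the 2-point pair | 81.5% | 84.3% | 2.8 |
| 0, 2, 1 | each 1-point pair | 23.1% | 37.4% | 14.3 |
| 0, 2, 1 | any significant pair | 83.2% | 84.9% | 1.7 |

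As the third arm moves between the two extremes, the gain for the 2-point pair stays between 2.8 and about 7.3 points, and the gain for any significant pair between 1.4 and 1.9. Separate two-sample t-tests give similar figures: for means 0, 2, 1 the 2-point pair goes from 80.8% to 84.3%.

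**5. Where the loss arises.** Compared with 1.7% tests and no gate, the gate costs at most 0.4 points (0.7 with two-sample t-tests). The rest comes from the stricter threshold. With pooled error, a pair needs an observed difference of 2.414 × 0.6 = 1.45 points at 1.7%, against 1.976 × 0.6 = 1.19 at 5%.

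**6. Limits of the 5% control.**
- *Unequal SDs.* Take illustrative SDs of 3, 3 and 2, with the two SD-3 arms equal and the third far away. Pooled-error pair tests at 5% then give 7.7% error; the plan's 1.7% with pooled error gives 3.1%. Separate-variance tests at 5% restore 5.0%. At SD 3 in every arm they keep nearly all the power: 89.0% for a 2-point pair with the third arm at an extreme.
- *Interim look.* Section 10.6 has an interim analysis at 50%, and 19.7 would stop the study for clear superiority. Assume the same tests at 25 and 50 per arm with no alpha allocation. Under the complete null the error is 7.2% as planned and about 8.5% with 5% pair tests. With two arms equal and the third far away it is 2.9% and about 8.3%.

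**The case against.** The strongest reply is that nothing here is broken. Sections 8.2 and 8.3 agree with each other, the error is controlled at a single final analysis, and the promised 80% is delivered even through the gate. Bonferroni is simple, and its unused margin absorbs some departure from equal variances and some of the damage from an unadjusted interim look. All of this stands, and it is why the point is an efficiency suggestion only.

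A reader might infer three stronger things, none of which the documents support:
- *That the double control leaves the trial underpowered or invalid.* The stated power reproduces, and the error is below 5% at one final analysis.
- *That about 14 points are lost on the design difference.* That figure belongs to a 1-point pair, half of what 8.2 sets out to detect, and power there is poor either way.
- *That the gate is the costly step.* It costs well under one point.

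The objection does not remove the point. The gain needs no extra patients, and the variance problem is met by using Welch tests instead of the pooled error. The interim and time-point questions need an answer whichever pairwise level is used.

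**Conclusion.** This is a cheap improvement, not an error. Keeping 1.7% behind the F-test forgoes about 3 to 7 points of power for the planned 2-point pair and about 14 for a 1-point pair. It forgoes less than 2 points for finding any difference at all. The gain is bought by using error the plan already permits: with two arms equal, the error rises from 1.7% to 5%.

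The conclusion rests on three groups, a 5% F-test, two-sided pair tests, approximately normal errors, SD 3 with 50 per arm, one outcome and one analysis. The size depends on the third arm's mean. If the SDs differ, Welch tests protect the case in which one pair is equal, while the ordinary F-test holds the complete null only approximately.

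**What to change.** In 8.3 and 10.7, replace the last sentence with: *If the overall F-test is significant at the 5% level, each of the three pairwise comparisons is tested at two-sided 5% with a two-sample (Welch) t-test (closed test for three groups). This applies to the named primary time point, at the final analysis only.* Do not prescribe the pooled ANOVA error for the pairs.

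Three things go with it:
- Name the primary time point. Section 8.2 lists both 0 and 10 minutes, and the 5% control covers one outcome.
- State whether efficacy is tested at the 50% interim and, if so, give that look its own alpha. Sections 10.8 (no stopping rules) and 19.7 (stop for clear superiority) have to be reconciled to answer this.
- Add to 8.2 that the 1.7% calculation is a conservative planning figure, so that it does not appear to contradict 8.3.

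The cost is a replaced sentence in two sections and a clause in 8.2, made before any comparative data are seen. The downsides are less margin if assumptions fail, and pairwise decisions that will not always match Bonferroni intervals. The F-test gate already allows such mismatches.

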9.0 Confidentiality, Privacy and Data Management

See the Research Data Plan Review Form

9.1 Confidentiality

9.1.1 Identifiers associated with data and/or specimens

9.1.1.1 Use of Codes, Master List

9.1.2 Storage of Data and/or Specimens

9.1.3 Access to Data and/or Specimens

9.1.4 Transferring Data and/or Specimens

9.2 Subject Privacy

10.0 Data and Safety Monitoring Plan

10.1 Periodic evaluation of data

The research coordinator will complete the appropriate report form and logs; assist the principal investigator to prepare reports and notify the IRB and any applicable reporting agencies of all unanticipated problems / adverse events.

The research coordinator and principal investigator will confirm that all adverse events are correctly entered in the AE log; be available to answer any questions concerning AEs; notify the IRB and any applicable reporting agencies of unanticipated problems and AEs as appropriate. All assessments of AEs will be made by a licensed medical professional who is an investigator on the research.

10.2 Data that are reviewed

Data to be reviewed includes incidence of adverse effects collected data.

10.3 Method of collection of safety information

Not applicable.

10.4 Frequency of data collection

Not applicable.

10.5 Individuals reviewing the data

Not applicable.

10.6 Frequency of review of cumulative data

There will be an interim analysis in this study after 50% of patients are enrolled and have completed all study requirements. Adverse events will be reviewed as they occur.

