10.7 Statistical tests

A one-way analysis of variance (ANOVA) model will be used to test whether changes in pain scores differ by study group. The outcome variable for the model will be the change in pain scores, and the independent variables will be indicators of each study group. The overall F-test for study group will be used to determine whether study groups differ with respect to mean changes in visual pain scores. If the F-test is significant, then follow up tests comparing each set of groups will be conducted using the Bonferroni-adjusted Type I error rate of 1.7%.

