10.8 Suspension of research

There will be no stopping rules in this study as all medications are FDA approved and safe for patient use.

If a patient, at any point in the course of their treatment demonstrates a significant adverse event related to the study medication, then the adverse event will be addressed.

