19.7 Stopping Rules

The study will be stopped if one method is found to be clearly superior or if there are adverse reactions.

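### Sections 10.8 and 19.7 conflict on stopping, and the 50% interim has no stated scope or rule, so the 5% overall error in 8.2 is not assured

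*Combined protocol and SAP*

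**What the plan says.** All of the following is current text in the combined protocol and SAP.

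- Section 10.6: "There will be an interim analysis in this study after 50% of patients are enrolled and have completed all study requirements". Its next sentence has adverse events reviewed as they arise. It gives no purpose, data scope, threshold or consequence for the interim.
- Section 10.8: "There will be no stopping rules in this study as all medications are FDA approved and safe for patient use". Its next paragraph concerns the handling of an individual patient's adverse event.
- Section 19.7: "The study will be stopped if one method is found to be clearly superior or if there are adverse reactions". Neither condition is defined, and the section does not refer to the 50% look.
- Section 10.2: "Data to be reviewed includes incidence of adverse effects collected data".
- Section 10.7, inside the monitoring plan, repeats the section 8.3 analysis: an ANOVA on change in pain and, if the F-test is significant, "follow up tests comparing each set of groups will be conducted using the Bonferroni-adjusted Type I error rate of 1.7"%. No level is given for the F-test, and the interim is not mentioned.
- Section 8.2 applies a Bonferroni level of 1.7% to three tests, "which holds the overall Type I error rate for the study at 5"%.
- Section 10.5, on who reviews the data, is marked not applicable, as is blinding in section 7.4.5. Section 10.1 assigns adverse-event checks to the coordinator and principal investigator. Section 16.5 has the team meeting regularly to look at data.

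**The concern.** The plan contains a mid-trial analysis, a clause that stops the trial for superiority and a clause that says no stopping rules exist. At about 75 patients, one team could stop on pain scores under 19.7 and another could decline to stop under 10.8, each following the document.

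It is also unclear whether the interim looks at efficacy. Section 10.2 points to safety data. Section 10.7, section 19.7 and the separate sentence in 10.6 on adverse events point to a pain comparison. If there is one, nothing limits who sees it: the study is unblinded, no reviewer is named for it, and the team reviews data regularly.

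Two things are at stake. The error statement in 8.2 counts three contrasts and no second look. And a stop on one contrast can end the trial with another contrast unsettled. If the meaning of clear superiority is settled only after pain data have been seen, the 5% cannot be defended.

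**Working it through.** **The plan's own figure.** Inputs from section 8.2: difference δ = 2, SD σ = 3, level 0.05/3 = 0.0167 (stated as 1.7%), power 80%. Sidedness is not stated; two-sided is assumed because a one-sided test would need only 40 per group.

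n per group = 2(z₁₋α/₂ + z₀.₈)²σ²/δ² = 2 × (2.394 + 0.842)² × 9/4 ≈ 47.1, so 48.

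The exact t calculation gives 49 per group and 81.3% power at 50. The stated 50 per group is therefore reproduced for a single analysis.

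**One contrast, two looks.** With 25 then 50 per arm, the two test statistics have correlation √(25/50) = 0.707. The chance of crossing two-sided 1.67% at either look is 2.9%, against 1.67% for one look.

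**The whole procedure.** This was simulated under these assumptions:
- normal change scores with SD 3, at one time point;
- equal arms, with looks at 25 and 50 per arm on accumulating data;
- F-test at 5% (not stated in 8.3 or 10.7), gating two-sided pairwise tests at 1.67% that use the pooled variance;
- at a stop, all three contrasts are read at 1.67%.

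Chance of any false pairwise claim when the arms do not differ:

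| Interim rule | Error |
|---|---|
| No pain comparison, or one that cannot stop the trial | 4.2% |
| Any contrast at unadjusted 1.7% stops the trial | 7.2% |
| One arm must beat both others at 1.7% | 4.4% |
| F-test and at least one pairwise p<0.001 | 4.2% |

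Two-sample t-tests in place of pooled ones give 4.0%, 6.8%, 4.2% and 4.1%.

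**Power for B vs A when B − A = 2.** Section 8.2 says nothing about where C lies, so a range is shown. The last two columns are for the boundary in fix option (b) (interim F-test p<0.001, at least one pairwise p<0.001, and one arm beating both others at 1.7%).

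| Position of C (assumed) | One look | Any-contrast stop | Option (b) | Trials stopped under (b) |
|---|---|---|---|---|
| Equal to A | 82% | 71% | 82% | about 14–15% |
| Midway | 81% | 80% | 81% | about 4% |
| Equal to B | 82% | 71% | 81% | about 1% |

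The loss under the any-contrast stop arises when the trial ends on a different contrast before B vs A is settled. The null error under option (b) is 4.2%. The estimate at such a stop is exaggerated: with C equal to A, the simulated mean of B − A at a stop is about 3.1 against a true 2.

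**Why option (b) requires beating both arms.** If B and C are both 2 points from A, a p<0.001 boundary on any one contrast stops 17% of trials. In only about 6% of those stops does one arm beat both others, so it would usually declare a superior method with no single winner.

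**The case against.** The strongest reply has four parts.

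1. Section 10.8 justifies itself by drug safety and then discusses adverse events, so it can be read as a safety statement only. That stands, and it removes the conflict with 19.7 on superiority. It does not remove the conflict on adverse reactions. One could say that 10.8 denies preset rules while 19.7 keeps discretion, but 19.7 is titled as stopping rules and is worded as something that will happen.
2. In a three-arm trial, clear superiority of one method most naturally means beating both others. The error is then 4.4%, with no power loss at the design effect when C equals A. This also stands. A reader might infer that the trial's error rate is 7.2%, or that any interim look at pain breaks the 5%. The documents support neither: a comparison that cannot stop the trial, a beats-both rule and a strict threshold all stay below 5%. The 7.2% needs an unadjusted stop on any single contrast.
3. The interim may be for safety only, as 10.2 suggests. That is possible, but 10.6 already has adverse events reviewed as they occur, and 10.7 places the pain ANOVA in the monitoring section. Equally, a reader might infer that an efficacy interim is planned; 10.7 does not mention the interim and 19.7 is not tied to the 50% look, so that is not established.
4. A reader might infer that an interim stop costs 11 points of power. That holds only if C equals A or B; with C midway the loss is about 1.5 points.

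**Conclusion.** The point holds as a contradiction in current text together with an undefined interim. As worded, 10.8 and 19.7 conflict on both grounds for stopping; reading 10.8 as safety-only leaves the conflict on adverse reactions. The 8.2 claim of 5% is sound for three contrasts at one final look. It is not assured if a pain comparison can stop the trial under a rule that the plan does not give.

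The size is conditional: error between 4.2% and 7.2%, and a loss of B-vs-A power of about 1.5 to 11 points under the least favourable rule. These figures rest on a 5% F-test, two-sided tests, normal scores, equal arms, one time point and exactly two looks. None of the last three is secured by the text on monitoring, and C's position is an assumption. The sample size is not at fault for a single analysis. This should be corrected before the 50% review, because it cannot be repaired credibly once pain data have been compared.

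**What to change.** Reconcile 10.2, 10.6, 10.7, 10.8, 16.5 and 19.7 before the 50% review. The sponsor should choose one option.

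**(a) No interim efficacy comparison.** State in 10.6 and 16.5 that pain scores are not compared between groups before the final analysis, and say what the 50% review does cover, in line with 10.2. State in 10.7 that the ANOVA is run once, at the end. Delete the superiority clause from 19.7. The 8.2 claim then holds for one final analysis of one named time point. The cost is the loss of the efficacy stop.

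**(b) Keep the efficacy stop and define it.** Define clear superiority as one arm beating both others at a prespecified strict boundary, for example interim F-test p<0.001, at least one pairwise p<0.001, and that arm better than each other arm at 1.7%. State the F-test level, name in 10.5 who sees the comparison, leave the final tests unchanged, and restate 8.2 as covering three contrasts and two looks. Align 10.8 with the retained stop and 16.5 with the restricted access. The cost is a stop that will rarely be used and an exaggerated estimate when it is.

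Either option takes a few sentences, needs no extra patients and leaves the final test levels as they are.

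Separately, the statements in 10.8 and 19.7 on stopping for adverse reactions must be reconciled. No safety rule is proposed here.
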